Study Protocol and Statistical Analysis Plan

Study Title: Musculoskeletal Plasticity After Spinal Cord Injury

NCT02622295

Document Version: 8/25/2022

Study Objectives

Patients with spinal cord injury (SCI) experience metabolic syndrome, diabetes, obesity, pressure ulcers, and cardiovascular disease at far greater rates than the general population. A rehabilitation method to prevent or reverse the systemic metabolic consequences of SCI is a pressing need.

The **purpose** of this study is to determine the dose of muscle activity that can enhance an oxidative muscle phenotype and improve clinical markers of metabolic health and bone turnover in patients with SCI. The **long-term goal** of this research is to develop exercise-based interventions to prevent secondary health conditions such as diabetes and to ultimately protect health-related quality of life (QOL).

Specific Aim 1: To compare changes in skeletal muscle gene regulation in individuals who receive high frequency (HF) active-resisted stance and low frequency (LF) active-resisted stance for 3 years.

Hypothesis 1: The expression of genes regulating skeletal muscle metabolism will support that HF and LF both instigate a shift toward an oxidative muscle phenotype. A novel finding will be that LF is a powerful regulator of oxidative pathways in skeletal muscle.

Specific Aim 2: To compare changes in systemic markers of metabolic health and bone turnover in individuals with SCI who receive HF or LF for 3 years.

Hypothesis 2: HF and LF will both reduce glucose/insulin levels and HOMA (homeostasis model assessment) score.

Secondary Aim: To measure subject-reported QOL using the EQ-5D survey metric.

Hypothesis 3: HF and LF subjects will show a trend toward improved self-reported QOL after 3 years. There will be an association between metabolic improvement and improved perception of QOL. These observations will support that this intervention has strong feasibility for future clinical translation.

Design

Population: Individuals with motor-complete spinal cord injury (SCI) (AIS A – B), 21 to 60 years of age.

Exclusion Criteria: Pressure ulcers, chronic infection, lower extremity muscle contractures, deep vein thrombosis, bleeding disorder, recent limb fractures, any comorbid disease known to affect bone metabolism (such as parathyroid dysfunction), pregnancy, anti-osteoporosis medications, Vitamin D supplements, Metformin or other medications for diabetes

Enrollment: Non-random assignment

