Study Arm 1: Acute gene regulation in response to single-session electrically induced exercise

Study Arm 2: Adaptations in gene regulation, metabolic markers, and subject-report metrics in response to up to 3 years of electrically induced exercise

Methods

Baseline Characteristics: Participants will provide information on age, sex, race, ethnicity, and level of SCI (quadriplegia, paraplegia)

Study Arm 1: Participants will undergo unilateral vastus lateralis skeletal muscle biopsy: they will be positioned in supine, the skin over the biopsy site will be sterilized, up to 3 mL of 1% lidocaine will be injected locally, and a 1/8th inch incision will be made with a scalpel. The biopsy needle will then be inserted and four cores of muscle (~ 20 mg) will be obtained from four passes of the needle through the same puncture site. The incision site will be closed with steri-strips or a butterfly bandage and the subject will be told not to perform electrical muscle stimulation or wet the area for 48 hours. Muscle specimens will be immediately processed for microarray analysis. Participants will then undergo a single session of electrically-induced exercise to the quadriceps and hamstrings muscles of the non-biopsied limb. Stimulating electrodes will be placed over the quadriceps and hamstrings muscles, and electrical stimulation will be given to induce an isometric closed kinetic chain knee extension moment. Participants will rest for 3 hours and then the vastus lateralis biopsy procedure will be repeated on the limb that performed electrically-induced exercise.

Study Arm 2: Participants will complete a baseline assessment including the biopsy procedure described above, completion of the EQ-5D self-reported quality of life survey, and venipuncture. Venous blood will be collected into vacutainer tubes with anticoagulant for glucose, kept on ice in dark conditions. The blood will be centrifuged and analyzed with a blood auto-analyzer. A portion of the blood sample will be tested via enzyme-linked immunosorbent assay (ELISA). Insulin and glucose values will be entered into the homeostasis model assessment equation (HOMA) to yield a HOMA score. After two weeks, participants will begin electrically induced exercise training. They will perform electrically induced exercise as described above for up to 3 years. At the conclusion of training, participants will undergo repeat biopsy, EQ-5D survey, and venipuncture.

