Outcome Measures: Microarray will be used to measure mRNA transcription levels for genes that regulate muscle atrophy (myostatin – MSTN), cellular adaptation to exercise (peroxisome proliferator-

activated receptor gamma coactivator alpha – PGC1-alpha), and muscle oxidative metabolism (pyruvate dehydrogenase kinase – PDK4, and succinate dehydrogenase-B – SDHB). Standard clinical assays will be used to measure levels of serum biomarkers for metabolism (fasting insulin, fasting glucose). Fasting insulin and fasting glucose will be used to calculate HOMA-IR, an index of insulin resistance. ELISA will be used to measure levels of osteocalcin, a biomarker of bone turnover. For the EQ-5D metric of health-related quality of life, self-reported numeric health state will be converted to Quality-Adjusted Life Years (QALY) using standardized tables.

Statistical Analysis Plan

Gene mRNA transcript levels will be expressed as Log_2 intensity (arbitrary units). Each blood biomarker will be expressed as its commonly-used clinical unit of measure (eg. mg/dL). EQ-5D health states will be expressed as QALY.

Change over time for each outcome measure will be assessed via repeated-measures one-way ANOVA. For study Arm 1, gene expression levels from the baseline biopsy will be contrasted to the 3 hour post-exercise biopsy. For study Arm 2, post-training values for all outcome measures will be contrasted to the baseline assessment point.

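### The Arm 2 analysis uses only participants with both a baseline and a post-training value, so non-random loss can bias the change, and loss cannot count against the feasibility conclusion

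*Combined protocol and SAP*

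**What the plan says.** **Assessments.** Under Methods, Study Arm 2, there is one baseline assessment and one repeat: "At the conclusion of training, participants will undergo repeat biopsy, EQ-5D survey, and venipuncture". No interim assessment is described. On duration: "They will perform electrically induced exercise as described above for up to 3 years".

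**Analysis.** The Statistical Analysis Plan states: "Change over time for each outcome measure will be assessed via repeated-measures one-way ANOVA". For Arm 2, "post-training values for all outcome measures will be contrasted to the baseline assessment point". It gives no analysis set, missing-data rule, expected loss or sensitivity analysis.

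**Feasibility.** Hypothesis 3, under Study Objectives, makes two predictions: "HF and LF subjects will show a trend toward improved self-reported QOL after 3 years" and "There will be an association between metabolic improvement and improved perception of QOL". It then concludes: "These observations will support that this intervention has strong feasibility for future clinical translation". The list of outcome measures contains no retention, adherence or completion measure.

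**The concern.** There are two linked problems.

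1. **Who is analysed.** A change score needs both values. The restriction to complete pairs is not written in the plan; it follows from the named method. If the chance of having a post-training value depends on the starting level, the mean change among complete pairs contains regression to the mean, even when training does nothing. If it depends on how the participant responded, the estimate is selected on the outcome itself. Training of up to 3 years followed by a second muscle biopsy gives ample opportunity for loss, and the plan does not argue that such loss would be random.

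2. **What feasibility rests on.** Both observations named in Hypothesis 3 can be made only in people who return for the final assessment. If many did not return, nothing in the plan would make the feasibility conclusion weaker.

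At stake are the Arm 2 estimates for HOMA, osteocalcin, gene expression and EQ-5D, and a statement about readiness for clinical translation.

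**Working it through.** **Inputs.** From the documents: two time points, repeated-measures one-way ANOVA, training up to 3 years. The documents give no sample size, SD, correlation, loss rate or alpha, so there is no figure of the plan's own to reproduce. Everything numerical below rests on assumptions, stated at each step.

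**Step 1: the method.** On 12 simulated pairs, the two-level repeated-measures ANOVA gave F = 1.3406, equal to the square of the paired t statistic. With two post-training values removed, the ANOVA routine rejected the data as unbalanced. The method needs complete pairs.

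**Step 2: bias when loss depends on baseline.** Let the baseline SD be 1, the post-training SD be R, the correlation ρ and the true change 0. Let m be the mean baseline of those with a post-training value, in SDs from the mean of all enrolled. Then

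bias of the paired change = (ρR − 1) × m.

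With ρ = 0.6 and R = 1 this is −0.4m. A logistic model links baseline to having a post-training value:

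- 20% loss, slope 0.5 per SD: m = 0.096, bias = −0.4 × 0.096 = −0.04 SD.
- 50% loss, slope 1.5 per SD: m = 0.530, bias = −0.4 × 0.530 = −0.21 SD.

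The sign shown is for loss of people with low baselines; it reverses if people with high baselines are lost. With random loss m = 0 and the bias is 0. Simulation with 24 enrolled gave the same biases, with two-sided 5% type I error between about 5.6% and 12%. An estimate that uses all baselines stayed within 0.01 SD of zero.

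**Step 3: loss related to the participant's own change.** Assume ρ = 0.5, 30% loss of those who changed least favourably, and a latent correlation of 0.5 between change and staying. The SD of change is √(2 × (1 − 0.5)) = 1.

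- Bias of complete pairs: 0.25 SD.
- Bias of the estimate using all baselines: 0.19 SD, so reduced but not removed.
- Type I error of the paired test under the same loss and latent correlation: about 9% with 10 enrolled, 15% with 20 and 27% with 40. Under random loss it stays at 5%.

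**Step 4: which likelihood model.** Take the most severe setting of Step 2 (ρ = 0.6, 50% loss, slope 1.5), large samples, and let R vary:

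| Post-training SD ÷ baseline SD | Complete pairs | Random intercept | Unstructured covariance |
|---|---|---|---|
| 1.0 | −0.21 | 0.00 | 0.00 |
| 1.5 | −0.05 | +0.23 | 0.00 |
| 0.6 | −0.34 | −0.16 | 0.00 |

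The formula agrees for complete pairs: (0.6 × 1.5 − 1) × 0.53 = −0.05 and (0.6 × 0.6 − 1) × 0.53 = −0.34. A random participant effect forces equal variances at the two times, and when they differ it can do worse than the paired test.

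**Step 5: feasibility.** Set side by side, the two observations in Hypothesis 3 each need a post-training EQ-5D, and the second also a post-training metabolic value. Neither involves the number enrolled. A retention proportion does: 14 of 20 is 70% (exact 95% CI 46% to 88%) and 8 of 20 is 40% (19% to 64%). These counts are illustrative.

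**The case against.** The best case for the plan has four parts.

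- **Early stoppers may be included.** Training is for up to 3 years and the repeat assessment comes when it ends, so someone who stops early can still be assessed. This stands. A reader might infer that the analysis covers only people who finished the programme; the documents do not support that. Only those with no post-training assessment are lost. The plan does not say whether early stoppers are called back.
- **Bias is not certain.** This also stands. A reader might infer that any drop-out biases the result. It does so only if loss is related to baseline or outcome, and the direction depends on who is lost. At the mild end of the assumed range (0.04 SD, type I error about 5.6%) the effect is negligible.
- **Feasibility is not a formal endpoint.** Hypothesis 3 is a prose expectation, and feasibility is neither an aim nor an outcome measure. A reader might infer a decision rule that any chance upward drift in quality of life would satisfy. The text does not support this: it names two observations together and sets no threshold for either, so no chance rate can be attached to it. The remaining point is narrower: the conclusion is stated, and the data named for it cannot reflect loss.
- **A mixed model is no cure-all.** Correct. It relies on data missing at random, and the random-intercept form adds an equal-variance assumption. The fix has to deal with both.

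**Conclusion.** The concern holds in a limited form. The planned Arm 2 contrast uses only participants with both values, and non-random loss **can** bias it. On the assumed inputs with loss linked to baseline (24 enrolled, correlation 0.6, equal SDs, no true change, 20% to 50% lost), the bias is 0.04 to 0.21 SD and the type I error about 5.6% to 12%. Loss linked to the participant's own change could do more. Because the documents give no sample size or loss rate, these figures show what is possible and do not predict what happened in this trial.

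The feasibility point needs no numerical assumption: the evidence named in Hypothesis 3 comes only from people with post-training data, so loss cannot weigh against the conclusion. The plan should be changed on both counts, though neither prevents the trial from running.

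**What to change.** 1. **Model.** Analyse each Arm 2 outcome with a likelihood-based repeated-measures model (REML, time as fixed effect, unstructured 2×2 covariance), including every enrolled Arm 2 participant's baseline. Do not use a random intercept alone. With no missing values the estimate equals that of the paired analysis.
2. **Missing data.** Define the Arm 2 analysis set. Compare the baselines of those with and without post-training values, and add a sensitivity analysis for loss related to the participant's own change.
3. **Feasibility.** Remove the inference from quality of life. Base any feasibility statement on the numbers enrolled, trained and assessed, with reasons for loss and an exact 95% CI for the proportion completing, with completion defined in advance. Add session adherence if attendance records exist; the documents mention neither such records nor a planned session count.
4. **Quality of life.** Replace the trend in Hypothesis 3 by the mean change with its 95% CI.

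**Cost.** SAP wording and some extra reporting; no added visits or participants. The model still assumes data missing at random, and the feasibility result may look less favourable than it would under the present wording.
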